2 PARTICIPANTS

2.1 Participants. Describe the general characteristics of the subject populations or groups, including age range, gender, health status, and any other relevant characteristics.

The unit of study and eventual randomization unit are the family planning clinics themselves. In 2014, there were 194 FP clinics in Mombasa County. Forty-three were public, while 151 were private, but worked with the DOH to dispense FP products provided at no cost by the government. Clinics ranged

from dozens to hundreds of clients per month. In total, the county had 110,682 FP clients in 2014, of whom 38,418 were new (mean 21 new clients/clinic/month). About 10% of new visits were post-partum.

In addition to FP clinics, there will be in-depth interviews conducted with FP clinic managers. These will likely be adults >18 years of age and both male and female.

2.2 Inclusion and exclusion criteria. Describe the specific criteria you will use to decide who will be included in your study from among interested or potential subjects. Define any technical terms in lay language.

Inclusion and Exclusion Criteria:

Clinics will be enrolled in the study though clinic managers and clinic staff will consent to participate in in-depth interviews. A set of family planning clinics will be enrolled with the goal of having a wide range of clinic sizes, degree of urbanity and performance level of the clinic. If clinics plan to be closed during the study period, they will be excluded. Additionally, if clinics are unwilling to be randomized or to participate in the SAIA intervention/approach then they will be excluded.

2.3 Prisoners. IRB approval is required in order to include prisoners in research, even when prisoners are not an intended target population.

a. Will you recruit or obtain data from individuals that you know to be prisoners?

For records reviews: if the records do not indicate prisoner status and prisoners are not a target population, select "No". See the [WORKSHEET: Prisoners](#) for the definition of "prisoner".

	No
	Yes

→ If yes, answer the following questions (i – iv).

i. Describe the type of prisoners, and which prisons/jails:

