After randomization, clinics allocated to the control arm will receive no further training or support from the study team. The only study team involvement at control facilities following randomization will be outcome ascertainment. At intervention facilities, the study team will train FP clinic staff on the SAIA intervention and support them during the active intervention phase shown in blue in Figure 8. After a second year of observation with minimal support in the intervention arm and no support in the control arm, the study team will again ascertain outcomes. Ownership of the SAIA intervention will transition to the MOH team during year two of the trial.

To understand acceptability, feasibility, complexity, and appropriateness of SAIA as an implementation strategy, we will conduct exit interviews following the Aim 1 trial.

Aim 2

Minimal Intervention Period during the Second Year of the Trial and Transition of the SAIA intervention to MOH ownership

We would like to know if SAIA training can produce a lasting effect without long-term support from the study team. This seems plausible, and cost-effective, given the success of expanded HIV testing in the ANC setting (11). The study team will train FP clinic staff on SAIA intervention during the first year of the study and then provide minimal support during the second year of the study to assess for sustainability of this approach (Aim 2). During year two, ownership of the SAIA intervention will transition to the Mombasa County Ministry of Health.

Aim 3

[figure not shown]

Figure 8. Study

We will perform a costing analysis, estimating incremental cost per outcome (e.g. new HIV diagnosis). We will also estimate cost to scale up, and perform a budget impact analysis (BIA) from the Kenyan DOH perspective. Our analysis will be conducted from the programmatic/payer (DOH) perspective. We will estimate economic costs in this analysis, including actual financial outlays and costs of donated and volunteer time (Table 1).

Table 1. Costing characteristics

Perspective	Programmatic perspective (e.g. NASCOP or Mombasa County DOH perspective) to determine the incremental costs and net benefits to anticipate whether the SAIA intervention is feasible.
Cost estimates	Intervention costs will include costs associated with the SAIA intervention, including the increased costs and benefits of additional newly diagnosed HIV-positive women started and retained on ART.

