Data collection	Cost data will be collected from the study budget, health facilities, published government information on labor costs, and health economics literature. These data will be used to complete intervention cost worksheets.
Primary outcomes	The incremental cost per new HIV-positive and HIV-negative individual identified
Discount rate	A discounting rate of 3% will be used, and varied from 0% to 5% in sensitivity analyses (66).
Time frame	Results will also be reported over a 1, 5, 10 and 15 year time frame.

Activity Based Micro-Costing Methods

We will estimate the incremental costs of implementing SAIA compared to standard procedures. Intervention costs will include costs associated with SAIA (start-up, personnel, transport, communication, consumables and overhead costs). Cost data will be collected from the study budget, clinic expense reports, published information on labor costs, and staff interviews. These data will be used to complete intervention cost worksheets at SAIA intervention and control facilities. Intervention clinic data will be collected during start-up, to capture the initial costs of program implementation, and again when the intervention is running at steady state. Costs will be categorized as fixed or variable. Variable costs indicate which costs could change (e.g. using free communication instead of standard telephone rates) and influence study estimates.

Time-and-Motion Studies

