Time-and-motion studies will be conducted over a two-week period at each site while the intervention is running at full capacity. A mentee trained in this process will collect data on the time required to complete each step of the SAIA process. Observing multiple visits will allow estimation of the average time taken for each step, and any time taken for research purposes (e.g. consent or assent of clinic staff members) will be subtracted from the estimated time needed for the intervention. Multiple providers and clients will be observed to capture the range of time required for a successful SAIA intervention. We anticipate that we would notify staff of the observation. If a staff member did not want to be observed, we would allow them to opt out. This could mean either avoiding observation in their work area, or not observing within that clinic, depending on what was required to respect the staff member's request. Through staff interviews and accounting for time available for the SAIA intervention, the number of patients supported by a clinic will be estimated. Together, the micro-costing data and the time-and-motion studies will be used to estimate the average cost of new HIV-positive and HIV-negative diagnoses.

Budget Impact Analysis

For BIA, we will consider direct program costs. Direct medical costs will be measured using established micro-costing methods, described above, to ensure that measurements of DOH costs reflect the opportunity cost of the resources used in delivering services. Further, the “top-down” approach of expense report collection will be compared with the “bottom-up” micro-costing approach to triangulate

and refine our cost estimates.

Data Analysis for Costing and Budget Impact Analysis

To the extent possible, we will use guidelines to facilitate standardization of cost data collection and reporting and to increase the transparency and generalizability of our results. For all key inputs and outputs, we will follow standard practices (57), including the guidelines by the Panel of Cost-Effectiveness in Health and Medicine (58). We will report on all costs using a recommended discount rate of 3% per year, as well as an alternative 5% discount rate and undiscounted inputs. We will conduct sensitivity analyses around key cost inputs to account for the uncertainty in our results.

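### The budget impact analysis is labelled DOH perspective but costed at economic value, with no rule that isolates what the DOH would have to spend

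*Combined protocol and SAP*

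**What the plan says.** All of this is in Section 5.1, mostly under Aim 3.

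- **Perspective.** The team will "perform a budget impact analysis (BIA) from the Kenyan DOH perspective". For the costing as a whole, "Our analysis will be conducted from the programmatic/payer (DOH) perspective". Table 1 gives NASCOP or the Mombasa County DOH as examples of the payer and ties the purpose to judging whether SAIA is feasible.
- **Cost basis.** In the same paragraph: "We will estimate economic costs in this analysis, including actual financial outlays and costs of donated and volunteer time". The BIA, named two sentences earlier, is not exempted.
- **BIA paragraph.** "For BIA, we will consider direct program costs". Direct medical costs come from the micro-costing already described, "to ensure that measurements of DOH costs reflect the opportunity cost of the resources used in delivering services". The top-down "approach of expense report collection will be compared with the" bottom-up micro-costing, in order to triangulate and refine the estimates.
- **Data sources.** "Cost data will be collected from the study budget, clinic expense reports, published information on labor costs, and staff interviews". Worksheets are completed at intervention and control facilities, and costs are classed as fixed or variable. No classification by payer is mentioned.
- **Grant-paid items.** Step 3 under Aim 1 lets the grant cover small material costs and tracks them into the costing and the BIA.
- **Setting.** Section 2.1 counts 194 family planning (FP) clinics in 2014: "Forty-three were public, while 151 were private, but worked with the DOH to dispense FP products provided at no cost by the government". The Preliminary Performance Review samples both kinds.

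**The concern.** A payer's budget impact answers one question: how much more will this payer have to spend if the programme is adopted? An economic costing answers another: what is the value of all resources the programme uses, whoever supplies them? Volunteer time belongs in the second answer but normally not in the first. The time of staff already on salary has an opportunity cost, but it need not mean new spending. The plan recognises the distinction, since it names money spent and donated time as separate components, but it does not carry it into the BIA.

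The result has a real user. Ownership of SAIA passes to the Mombasa County Ministry of Health in year two, and Section 1.5 promises both a scale-up cost and a DOH budget impact. If the BIA total mixes resources the DOH would fund with resources it would not, a reader may take it as a spending forecast and reach the wrong view on affordability.

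**Working it through.** The plan states no cost, budget or donated-time figure, so there is no result to reproduce. The check sets the provisions side by side and then asks what can be said about size.

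**1. Is the BIA covered by the economic-cost rule?** The rule applies to the Aim 3 analysis generally, and the BIA paragraph does not repeat the reference to donated and volunteer time. But that paragraph sets opportunity cost as its own basis for DOH costs and takes its direct medical costs from the shared micro-costing. The economic valuation is therefore stated for the BIA itself as well as inherited.

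**2. Does anything convert economic cost to DOH outlay?** Three provisions could do so:

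- Limiting the BIA to direct program costs narrows what is counted, but does not say who pays for it.
- Expense reports are collected, but only to cross-check and refine the estimates. No expenditure-based result is specified.
- The fixed/variable split concerns how costs could change, not who bears them.

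None of them separates out DOH financial cost.

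**3. Does the payer matter here?** 43 + 151 = 194, which agrees with the stated total, and 151/194 = 77.8% of clinics are private. The documents say these clinics dispense free government FP products. They do not say who pays their staff or overhead. So the treatment of private-clinic resources needs a rule. The 77.8% is a count of clinics in 2014; it is not a share of cost, of clients or of the trial sample.

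**4. Size and direction.** Let *B* be the BIA total as planned and *D* the financial cost the DOH would bear at scale-up. Let *s* be the share of *B* that the DOH would not bear, and *m* the share of *D* that *B* leaves out. The part common to both is *B*(1 − *s*) = *D*(1 − *m*), so

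*B*/*D* = (1 − *m*)/(1 − *s*).

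The documents give neither *s* nor *m*. The values below are assumptions for illustration only.

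| *s* | *m* | *B*/*D* |
|---|---|---|
| 0% | 0% | 1.00 |
| 10% | 0% | 1/0.90 = 1.11 |
| 20% | 0% | 1/0.80 = 1.25 |
| 30% | 0% | 1/0.70 = 1.43 |
| 50% | 0% | 1/0.50 = 2.00 |
| 0% | 30% | 0.70/1 = 0.70 |
| 30% | 30% | 0.70/0.70 = 1.00 |

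Volunteer time in the total raises *s*. Any study-team training or support that the DOH would have to take over but that was not counted raises *m*. The ratio can fall on either side of 1.

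**The case against.** The strongest defence is that the plan already has most of what is needed. Money spent is named as a distinct component, expense reports are collected, the BIA speaks of DOH costs and direct program costs, and undiscounted results are promised. An outlay-based BIA could be tabulated from these data. Valuing donated or grant-paid inputs is also defensible, because a payer taking over a programme may have to replace them. And the primary costing outcome in Table 1 is the incremental cost per individual identified, for which economic costing is suitable.

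Much of this stands, and it rules out several stronger readings that a reader might infer:

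- **That the BIA cannot show DOH outlay.** The components may allow it. What is missing is a commitment to separate and report it.
- **That private-clinic staff and overhead will be charged to the DOH.** No section says so. It is an inference from mixed sampling and worksheets with no payer field.
- **That the budget will be overstated.** The direction is not established, because grant-funded inputs may become DOH costs after handover.
- **That the scale-up budget should be weighted 43:151.** The plan does not say that scale-up covers all 194 clinics, and clinic volume varies from dozens to hundreds of clients a month.
- **That only items the DOH paid for during the trial should count.** That would drop grant-funded inputs, including materials the plan tracks into the BIA, and could understate the budget.

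The defence does not remove the mismatch. The stated cost basis is not the payer's spending, and no rule turns one into the other. Being able to derive the right figure is not the same as planning to report it.

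**Conclusion.** The point holds as a mismatch between the question and the cost basis. The BIA is set from the DOH's perspective but valued at economic cost, with no rule that isolates DOH financial outlay. Followed as written, it gives a figure that need not equal what the DOH would have to spend. Neither the size nor the direction of the gap can be found from the documents, and the ratios in the table rest wholly on assumed shares. The conclusion rests on two readings of the text: that the Aim 3 cost basis extends to the BIA, which the BIA paragraph's own reference to opportunity cost supports, and that expense reports serve only as a cross-check, which is the only use the plan gives them. The cost per individual identified is not affected.

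**What to change.** 1. **Tag the worksheets.** On the cost worksheets already planned, mark each line as financial or economic and by who would pay at scale-up: DOH, private clinic owner, continuing donor or volunteer. Do not tag by who paid during the trial.
2. **Define the BIA total.** Base the BIA and the scale-up budget on the financial costs the DOH would bear. Include grant-funded training, support and materials that it would have to take over. Exclude volunteer time and private-clinic resources that it would not fund.
3. **State the scenario.** Say which payer and which clinics the scale-up covers, and show public and private clinics separately. Where it is uncertain who would pay, vary that in the sensitivity analyses already planned.
4. **Name the reported version.** Undiscounted figures are already promised; state that they are the BIA result.
5. **Keep economic costs** for the incremental cost per individual identified, and label the two totals as answers to different questions.

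The cost is one worksheet column, one extra table and a line explaining why the totals differ. Payer is best recorded when costs are collected. The plan collects start-up costs first, and Section 5.1 reports that Aim 2 began in February 2020, so any lines already recorded would need to be tagged afterwards.

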Disclaimer: Due to restrictions on human subject research as a result of the COVID-19 pandemic, most activities for Aim 2, which began in February 2020, were on hold between March and August 2020. Activities resumed in September 2020, but were interrupted again by a strike, in response to unpaid wages and lack of PPE in the context of the COVID-19 pandemic. This has led to a number of our FP clinics being unable to participate in the trial for portions of the original 12-month period described in the Aims and Study Procedures. As a result, Aim 2 data collection will be extended an additional 6 months, for a total of 18 months of data collection for Aim 2.

5.2 Data variables. Describe the specific data you will obtain (including a description of the most sensitive items). If you would prefer, you may upload a list of the data variables to the **Supporting Documents** SmartForm instead of describing the variables below.

The primary outcome will be the proportion of eligible (not known HIV+) new FP clients who are tested for HIV during the evaluation periods at the end of 12 months of SAIA training and following an additional year in which intervention clinics are encouraged to continue to implement the SAIA intervention with minimal support from the study team. The secondary outcome will be the proportion of new FP clients who are counseled about HIV testing. When data are not filled, we will assume the counseling or testing has not been done. While we recognize that there are few variables available in implementation research datasets (e.g. clinic size, public/private, rural/urban), these variables will be collected for comparison of the randomization arms to assess balance across intervention groups.

Our primary analysis will follow the intent-to-treat principle. The proportion of eligible new FP clients tested for HIV and the proportion of new FP clients counselled about HIV testing will be compared in intervention versus control facilities using generalized estimating equations with a binary link, clustered by clinic. Because there will be more than a year between the first and second assessments, we anticipate that these will take place as separate analyses, as they are completed.

5.3 Data sources. For all types of data that you will access or collect for this research: Identify whether you are obtaining the data from the subjects (or subjects' specimens) or whether you are obtaining the data from some other source (and identify the source).

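### Aim 3 names uncertainty analyses for cost inputs and the discount rate only; no named method carries sampling error in the difference in diagnoses into the incremental cost per diagnosis

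*Combined protocol and SAP*

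**What the plan says.** Section 5.1, Aim 3, Table 1 gives the primary outcomes as "The incremental cost per new HIV-positive and HIV-negative individual identified". Two passages point to a comparison between arms. The micro-costing paragraph says "We will estimate the incremental costs of implementing SAIA compared to standard procedures", and the cost row of Table 1 covers SAIA costs "including the increased costs and benefits of additional newly diagnosed HIV-positive women started and retained on ART". Section 1.5 plans the cost per new diagnosis both for the supported phase and for the later phase.

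On uncertainty, the paragraph on data analysis for costing and budget impact says "We will conduct sensitivity analyses around key cost inputs to account for the uncertainty in our results". Table 1 and the same paragraph also vary the discount rate from 0% to 5% around 3%. The paragraph adds a general commitment, "For all key inputs and outputs, we will follow standard practices (57", and goes on to cite a cost-effectiveness panel guideline.

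Clustering appears in Section 5.2. There the proportions tested and counselled are compared "using generalized estimating equations with a binary link, clustered by clinic", separately at each assessment.

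**The concern.** A cost per additional diagnosis has two uncertain parts. The sentence on uncertainty offers a cost-side method for the results as a whole, yet the denominator is most naturally a difference estimated from 24 clinics. Varying costs or the discount rate rescales the numerator. It cannot show whether the difference in diagnoses is distinguishable from zero.

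The two outcomes differ in where the missing error lies. HIV-negative diagnoses are close to the number tested, so their error is mainly between-clinic variation in testing. HIV-positive diagnoses are rare, so simple count error matters more.

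A health department would use these ratios beside the scale-up cost and the budget impact analysis. As the plan is written, nothing ties the precision of the effect to the ratio in either phase.

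**Working it through.** The plan has no interval or expected value for the ratio, so there is no figure to reproduce. The first check is of the text and the second illustrates the size.

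**Text.** Apart from the cost-input and discount-rate analyses, the Aim 3 passages compare top-down with bottom-up costs, observe a range of staff times and report several time horizons. All of these concern cost or horizon. No bootstrap, probabilistic analysis, interval for a ratio, or variation of the number of diagnoses is named. The Section 5.2 model covers proportions tested and counselled, not diagnoses, and is not tied to Aim 3.

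**Inputs.**
- Clinics: 12 per arm (Section 1.5).
- Volume: 38,418 new clients over 194 clinics (Section 2.1) is 198 per clinic-year, or 12 × 198 = 2,376 per arm-year. Equal volumes are assumed.
- Tested: 20% versus 35%, borrowed from Section 1.8a, where these are visits at which testing was offered in another study. 20% versus 60% is an assumed larger effect.
- Positivity among those tested 4%, and ICC 0.05 or 0.10: assumed.
- Incremental cost: positive and held fixed.

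**Formula.** Let n = 198, p be the proportion tested, f the positivity (or 1 minus it for HIV-negative), and q = pf. Then:
- difference = 12n·f·(p1 − p0)
- variance = sum over arms of 12n·q(1 − q) [count] + 12n(n − 1)·f²·ICC·p(1 − p) [between-clinic]

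The 95% limits use t with 22 degrees of freedom, 2.074. With cost fixed, the ratio relative to its point estimate runs from difference/upper limit to difference/lower limit. It has no finite upper limit if the lower limit is zero or below.

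**A. HIV-positive, 20% versus 35%, ICC 0.10.**
- Difference: 2,376 × 0.04 × 0.15 = 14.3.
- Count: 2,376 × (0.014 × 0.986 + 0.008 × 0.992) = 51.65.
- Between-clinic: 12 × 198 × 197 × 0.0016 × 0.10 × (0.2275 + 0.16) = 29.02.
- SD: √80.67 = 8.98. Interval: 14.3 ± 18.6, or −4.4 to 32.9.
- Ratio: 14.3/32.9 = 0.43 times, with no finite upper limit.

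**B. HIV-positive, 20% versus 60%, ICC 0.05.**
- Difference: 2,376 × 0.04 × 0.40 = 38.0.
- Variance: 74.51 + 14.98 = 89.49; SD 9.46. Interval: 18.4 to 57.6.
- Ratio: 0.66 to 2.07 times.

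| Scenario | Outcome | Difference (95% limits) | Ratio to point estimate | Count share of variance |
|---|---|---|---|---|
| A | HIV-positive | 14.3 (−4.4 to 32.9) | 0.43 to unbounded | 64% |
| A | HIV-negative | 342.1 (66.9 to 617.4) | 0.55 to 5.11 | 5% |
| B | HIV-positive | 38.0 (18.4 to 57.6) | 0.66 to 2.07 | 83% |
| B | HIV-negative | 912.4 (709.4 to 1,115.3) | 0.82 to 1.29 | 10% |

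**Sensitivity.** With positivity at 1%, 2%, 4% or 6% and ICC 0.05 or 0.10, the same formula gives an HIV-positive interval that includes zero in all eight cases at 20% versus 35%. At 20% versus 50% it does so only at 1% positivity. At 20% versus 60% it never does, though at 1% and ICC 0.10 it only just clears zero. At the mean of 21 new clients a month printed in Section 2.1 (252 per clinic-year), A becomes 18.1 (−3.9 to 40.2) and B becomes 48.4 (25.7 to 71.0), or 0.68 to 1.88 times.

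These formulas ignore the restricted randomisation. A simulation that took the best 10% of 200 allocations, with an assumed baseline-to-follow-up correlation of 0.7, cut the HIV-negative SD in scenario A from 132 to 99. At 20% versus 35%, the HIV-positive range still reached zero in 13 of 16 clustered scenarios, against 15 of 16 without restriction.

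**The case against.** A reader might infer that the team will ignore sampling error. The documents do not show that. They show that no method is named, in an ethics application that asks for lay language, beside a commitment to guidelines on inputs and outputs. Diagnoses are an output, and those guidelines may require an effect-side analysis. This stands as a limit on the claim. It does not remove the point, because the sentence the plan does write on uncertainty is confined to costs.

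A reader might also infer that effect uncertainty is unmeasured throughout. That goes too far. The Section 5.2 model, run at both assessments, addresses between-clinic variation in testing, which is 90% to 95% of the HIV-negative variance in the scenarios above. What is missing there is the link to Aim 3. For HIV-positive diagnoses the count error is missing as well.

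Aim 3 carries no hypothesis, and the micro-costing and time-and-motion data "will be used to estimate the average cost of new HIV-positive and HIV-negative diagnoses", so the denominator could be partly modelled. That is fair: the between-arm ratio is the most natural reading, not a stated estimator. The word incremental and the comparison with standard procedures still favour it.

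**Conclusion.** The point holds in this form: the plan names no method that carries sampling error in the difference in diagnoses into Aim 3's primary ratios. This does not depend on any assumed number.

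The size does depend on assumptions. Positivity, ICC, effect size, equal volumes and fixed cost are all mine, and the documents give no values to replace the first three. An unbounded ratio should not be read as the general result. In the 12-month scenarios it arises only for HIV-positive diagnoses, and only with a modest effect or low positivity. The HIV-negative ranges are finite throughout, and at 20% versus 60% with 4% positivity the HIV-positive range is finite too, though about threefold wide (2.07/0.66 = 3.1). A shorter evaluation window, which Section 5.1 leaves open, would mean fewer events and wider ranges.

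Nothing here affects the hypotheses of Aims 1 and 2.

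**What to change.** Extend the sentence on cost-input sensitivity analyses with text such as:

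> In addition to the cost-input and discount-rate analyses, the between-arm difference in HIV-positive and in HIV-negative diagnoses, standardised to new-client volume and to the months each clinic contributed, will be reported for each trial phase with a 95% interval that respects clustering by clinic (for example, a clinic-level bootstrap within arm with a small-sample correction). This uncertainty will be carried into the incremental cost per diagnosis and shown on the cost-effect plane, with costs held fixed and varied one way where clinic-specific costs are not available. Where the interval for the difference includes zero, the difference and the plane will be reported, and the ratio will be described as not bounded above (negative values possible).

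Standardisation matters most in the second phase. The Section 5.1 disclaimer says some clinics could not take part for portions of it, so raw count differences could reflect closures.

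The cost is a little more analysis. Testing and HIV status are already taken from the registers in both arms, and no new cost data are required. The intervals will be wider than cost-only ranges and may be somewhat conservative under the restricted randomisation. In simulation, a corrected clinic bootstrap covered 95% to 97% for HIV-positive and 96% to 99% for HIV-negative differences.
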